## **Conflict of interest:**

There are no conflicts of interest. Dental implants, surgical guides were supplied free of charge by Dentsply Implants (M4 Implant MIS MF4-10330).

#### Date: 15 February 2023

**Trial registration:** Palestinian Health Research Council ethical approval attains from the Helsinki committee trial registration number (PHRC/HC/1242/23) at date of registration in it's meeting on 23/02/2023.

#### ABSTRACT

**Aim:** to evaluate the accuracy of tooth-supported fully-guided surgery to free-handed, countersink surgery in the posterior maxilla and mandibular of partially edentulous patients by using CBCT image after placing implant and superimposed it with pre-operative CBCT.

## Materials and methods:

A total of 30 implants of the same brand and type (M4 MIS Dentsply, Germany) were placed in15 partially edentulous volunteers in need of implantation in the mandible or maxilla or both. All cases were digitally planned using data from cone beam computed tomography, and the comparison of the planned and actual implant positions was performed using a medical image analysis software (blue sky plan 4). Post-op. CBCT was used for nine measurements representing the deviations in angles, implant shoulders and apexes. The outcome parameter was angular deviation (AD, degrees), crestal global deviation (CGD, mm), vertical linear deviation (VLD, mm), lateral linear deviation (LLD, mm), apical global deviation (AGD, mm), apical vertical deviation (AVD, mm), apical lateral deviation (ALD, mm), distance from maxillary sinus and distance from inferior alveolar nerve. Statistical analysis was performed using Fisher's exact test to compare the proportion between groups and Chi square test to test the relationship between two categorical variables.

Keywords: Countersink guided, Quasi experimental study, fully guided, Accuracy, partially edentulous.

**Trial registration:** Palestinian Health Research Council ethical approval attains from the Helsinki committee trial registration number (PHRC/HC/1242/23) at date of registration in it's meeting on 23/02/2023.

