## MATERIAL & METHODS

Inclusion criteria were as follows:

- Partially dentate adults with at least 6 remaining teeth
- The anticipated presence of sufficient bone volume allowing for implant placement with no simultaneous bone grafting
- Extractions within 2 months of welding.
- Want the missing tooth to be replaced by an implant
- Adequate related attached mucosa was found
- Mouth opening  $\geq$  40 mm
- Good oral hygiene
- Good general health

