#### Study design:

Researcher adopted pre and post Quasi-Experimental study design to fulfill the research objectives quantitatively. The Quasi-Experimental design is a popular design used in research. Pre/post-test design is a type of quasi-experimental study, in which an easily applied intervention can be studied in relationship to the group of subjects in the study. Conclusion Because the research design has problems that the validity of prepost and type study is not easily satisfied, we cannot expect it, but we can obtain associations in outcome measures in this popular research design by choosing randomization, controlling inner and external bias, and correctly applying simple statistics.

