#### **Data Collection procedure:**

#### **Analysis method:**

Free hand (countersink guided) and surgical guide surgeries were carried out by a parallel surgical kit (Dentsply®, MIS, M4, Germany), following the manufacturer's recommendations. The surgical guide surgeries were carried out using a dedicated (Dentsply®, MIS, M4 Germany) following the above-mentioned surgical plan. Both of the implants were performed for the same patient, on the same day and with the same devices. One implant per side was placed free hand, countersink guided and the other side with a computer-assisted implant guide.

With Blue Sky Plan 4 (Blue Sky Bio, Grayslake, IL, USA) software, the post-operative fixture was extracted as an STL file by segmentation the DICOM file of the CBCT taken after surgery used 3D slicer program as show in Figure 1.

Figure 1: show segmentation the DICOM file of the CBCT taken after surgery used 3D slicer program.

Then, the STL file post-operative fixture imported to Blue Sky Plan 4 program and superimposing with planned fixture on the CBCT on the planned implant location before surgery as presented in Figure 2.

Figure 2: show import the DICOM file post-operative fixture to Blue Sky Plan 4 program and superimposing with the CBCT which have the planned implant location before surgery.

More than twenty points marked on the two images using a point-based automatic image registration algorithm to ensure correspondence as show in Figure 3.

Figure 3 : aligned using a point-based automatic image registration algorithm.

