#### Measure the deviation for each parameter:

The definitions concerning accuracy outcome measures are as follows: The primary outcome was angular deviation defined as the angle closed by the principal axis of the planned implant and the principal axis of the inserted implant in degrees. The secondary outcomes were crestal global deviation; the distance between the center of the coronal end of the planned and the inserted implants in millimeters, apical global deviation; the distance between the apical endpoints of the planned and the inserted implants in millimeters, and vertical linear deviation ; the distance between perpendicular line on the hexagon of planned implant and another line draw parallel to it on the hexagon of actual implant in millimeters, lateral linear deviation; the distance between vertical line on the long axis of planned implant and another line draw parallel to it on the long axis of actual implant in millimeters, apical vertical deviation ; the distance between perpendicular line on the apex of planned implant and another line draw parallel to it on the apex of actual implant in millimeters, apical lateral deviation ; the distance between vertical line on the long axis of planned implant and another line draw parallel to it on the long axis of actual implant in millimeters, Two anatomical parameters were added to these ones : the distance from the inferior alveolar nerve (IAN) and the distance from the maxillary sinus (MS).

Primary outcome is Angular deviation of the final position to the planned implant position. Meanwhile, secondary outcomes are described by the following eight measurements.

Figure 4: Deviation parameters between the planned implant position (blue) and placed implant position (yellow): (a) Lateral Linear deviation (mm); (b) Vertical Linear deviation (mm); (c) Global Crestal deviation (mm); (d) Apical Lateral deviation (mm); (e) Apical Vertical deviation (mm); (f) Apical Global deviation (mm); a, Angular deviation (degree). (Ngamprasertkit et al., 2022)

The real measurements of the primary and secondary outcomes using Blue Sky Plan 4 Software are presented in Figure 5.

linear deviation (mm); (e) lateral linear deviation (mm); (f) crestal global deviation (mm); (g) apical vertical deviation (mm); (h) apical global deviation.

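### Pairs of implants that span both jaws are not excluded, and the analysis neither separates technique from jaw nor sets denominators for the nerve and sinus distances

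*Combined protocol and SAP*

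**What the plan says.** The sample is described in the abstract's Materials and methods: "A total of 30 implants of the same brand and type" were used, and they "were placed in15 partially edentulous volunteers in need of implantation in the mandible or maxilla or both". The stated aim covers work "in the posterior maxilla and mandibular of partially edentulous patients".

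The section on data collection and analysis method sets up a within-patient comparison: "Both of the implants were performed for the same patient, on the same day and with the same devices". Technique is tied to side and to nothing else: "One implant per side was placed free hand, countersink guided and the other side with a computer-assisted implant guide".

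The inclusion criteria refer to one missing tooth ("Want the missing tooth to be replaced by an implant"). Neither they nor the exclusion criteria say anything about jaw or about a matching second site. Randomization appears only in a general remark under Study design ("by choosing randomization, controlling inner and external bias, and correctly applying simple statistics"), with no method and no link to side or jaw.

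Angular deviation is the primary outcome. Among the other measurements are two anatomical ones: "the distance from the inferior alveolar nerve (IAN) and the distance from the maxillary sinus (MS"). The Data Analysis section allows independent or paired t-tests, or nonparametric tests. It has no jaw term, no stratification by jaw and no rule for a pair with one implant in each jaw.

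**The concern.** A split-mouth comparison works because the two sites in a patient are alike except for the technique. If one site is in the maxilla and the other in the mandible, the within-patient difference is the technique effect plus or minus the jaw effect, and that pair alone cannot separate them. Specifying opposite sides does not prevent this: upper right against lower left meets the description.

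Two things are at stake. First, the angular-deviation contrast is shifted if one technique falls more often in one jaw, and it is noisier even if the techniques are balanced over jaws. The Introduction gives some reason to think about balance, since it links the countersink method to hard bone. Whether bone differs systematically between the jaws in these patients is an assumption, but with no allocation rule the choice of site could follow it. Second, the nerve distance applies only to mandibular implants and the sinus distance only to maxillary ones, so a cross-jaw patient supplies one value of each, under different techniques.

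**Working it through.** **Implants per patient.** Inputs from the abstract and the procedure section: 30 implants, 15 patients, at least one implant per technique in each patient. 15 × 2 = 30, which reproduces the plan's total. Every patient needs at least 2 and the mean is 30/15 = 2, so every patient has exactly 2. If m patients had 4 implants (a pair in each jaw), 4m + 2(15 - m) = 30 gives m = 0. No patient can therefore contribute a same-jaw pair in both jaws.

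**Shift in the primary contrast.** None of the following is in the documents; all are assumptions. Let k of the 15 pairs be cross-jaw, let the jaws differ by d degrees in angular deviation, and let p be the fraction of cross-jaw pairs with the guided implant in the jaw with the larger deviation. For guided minus free-hand:

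shift in mean difference = (k/15)(2p - 1)d

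| k | same-jaw pairs left | shift at p = 1 |
|---|---|---|
| 0 | 15 | 0 |
| 1 | 14 | 0.07d |
| 3 | 12 | 0.20d |
| 5 | 10 | 0.33d |
| 8 | 7 | 0.53d |

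With k = 5 and p = 0.8 the shift is (5/15)(0.6)d = 0.20d. With p = 0.5 it is 0. An odd k cannot split evenly: at k = 5 the nearest split is 3 to 2 (p = 0.6), giving (5/15)(0.2)d = 0.07d. The difference in means is the same in a paired and an unpaired test, so the shift applies to either.

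**Added variance.** The jaw contribution to a paired difference is 0 in same-jaw pairs and +d or -d in cross-jaw pairs. Its variance is (k/15)d² minus the squared shift. When balanced this is (k/15)d², for example 5/15 = 0.33d² at k = 5.

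**What a jaw term recovers.** Code each pair s = 0 if same-jaw, and +1 or -1 by direction if cross-jaw. Regress the paired difference on s; the intercept is the technique effect. With residual variance v, the variance of the intercept is v·Σs²/(15Σs² - (Σs)²). With Σs² = k and Σs = k(2p - 1), this equals v/(15 - k(2p - 1)²). At k = 5:
- p = 0.5: 15 - 0 = 15 effective pairs
- p = 0.8: 15 - 5 × 0.36 = 13.2
- p = 1: 15 - 5 = 10, the same as using same-jaw pairs only

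The technique effect can be estimated unless all 15 pairs are cross-jaw in the same direction.

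**Nerve and sinus distances.** Same-jaw pairs number 15 - k and are shared between the two structures. With k = 0 and an even split, each has 15/2 = 7.5 pairs (7 and 8 in practice). With 5 mandibular, 5 maxillary and 5 cross-jaw pairs, each has 5 complete pairs. The number of implants per structure is 5 × 2 + 5 = 15, against 30/2 = 15 when k = 0. Pairing is lost, not measurements. With all 5 cross-jaw pairs in one direction, the implants for one structure divide 10 to 5 by technique.

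If the nonparametric option were used on 5 complete pairs, the smallest exact two-sided signed-rank p-value is 2/2⁵ = 0.0625, above the plan's 0.05. With 7 pairs it is 2/2⁷ = 0.016. The plan does not state sidedness; two-sided is assumed.

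**The case against.** The abstract's wording on both jaws describes what volunteers needed, not where their two study implants went. A patient needing treatment in both jaws may have had both study implants in one jaw, and the phrase about sides fits opposite sites in one arch equally well. This stands: k may be 0. It does not remove the gap, because nothing in the criteria or the procedure rules cross-jaw pairs out, and the analysis would not deal with them if they occurred. The singular in the tooth criterion carries little weight either way, since read literally it conflicts with any two-implant design.

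A reader might infer that technique is fully confounded with jaw in this trial. The documents do not support that. Aliasing is complete only inside a cross-jaw pair; over the trial it is partial, and the shift has expectation zero if technique is assigned at random over jaws. The extra variance would remain.

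A reader might also infer that cross-jaw patients give no comparison at all on the nerve and sinus distances, or that pairs fall from 15 to 5. Both overstate. The Data Analysis section includes an independent t-test, which can use unpaired values, and the two structures together can never have more than 15 pairs. In the worked example the fair comparison is about 7.5 against 5.

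Finally, making same-jaw pairs the main contrast would discard up to k of only 15 pairs after treatment. That objection also stands and shapes the fix.

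**Conclusion.** The concern holds as an unhandled possibility, not as a demonstrated bias. The count of exactly two implants per patient, one per technique, follows from the plan's own figures, as does the absence of any same-jaw requirement or jaw adjustment. For angular deviation, the size is (k/15)(2p - 1)d in the mean and up to about (k/15)d² in the variance of paired differences. Because k, p and d are all missing from the documents, no value in degrees can be given; the p = 1 figures are worst cases. For the nerve and sinus distances the effect is fewer complete pairs, with denominators that the plan does not state. If every pair proves to be same-jaw, the confounding falls away and only those denominators need reporting.

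**What to change.** If recruitment is still open, add to the inclusion criteria that each patient has two posterior sites in the same jaw, one on each side.

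For patients already treated (the text reports placement in the past tense):
- Classify each pair as same-jaw or cross-jaw from the existing CBCT, and report k and its direction by technique.
- Keep all 15 pairs in the main angular-deviation contrast, using a within-patient analysis with a jaw term. If k = 0 the term drops out.
- Show same-jaw pairs only as a sensitivity analysis.
- Compare the nerve distance among mandibular implants and the sinus distance among maxillary implants, stating the number of implants and of complete pairs for each.

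The cost is a slightly smaller eligible pool if enrolment continues, one extra model term (residual degrees of freedom for the paired differences go from 15 - 1 = 14 to 15 - 2 = 13), and smaller stated denominators for the two anatomical outcomes. No new imaging or procedure is needed.

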#### **INTRODUCTION**

The successful establishment of a dental implant not only depends on osseointegration but also on the function and aesthetics of the final prosthesis (Bell et al., 2018; Motta et al., 2016; Smitkarn et al., 2019). Many of the investigations concerning guided implant surgery had different approaches to the factors that could affect how precise the surgery will be. Dental implants have proven to offer high survival and clinical success rates in various indications (De Angelis et al., 2017; Derks et al., 2015). For this reason and under this scenario, present implant dentistry has been concentrating on improving the treatment plan, so that an aesthetic result is a new variable.

Precise three-dimensional (3D) positioning of the implant is needed for the best esthetic results (Ruppin et al. 2008; Tahmaseb et al. 2014). The implant should be placed prosthetically, and taking into consideration the anatomy and bone availability. In addition to esthetics, precision in placement can assist in reducing biologic/technical complications (Canullo et al.; Cassetta et al.).

Among the surgical guide protocols, two common design protocols, fully guided and free hand, countersink guided, are often mentioned in relation to their effects on accuracy. Fully guided surgery entails the surgical guide guiding all actions with guide sleeves, from the first drilling through the implant insertion. On the other hand, countersink guided surgery is used especially in hard bone, to provide passive seating of the implant neck. These special countersink drills are adapted to enlarge the crestal zone into thick cortical bone.

However, until now there is no clinical study specifically addressing the accuracy of countersink guided implant placement, which is supported by the implant industry. One single randomized clinical trial (Younes et al., 2018) investigated the accuracy of FH, PG, and FG implant placement procedures.

In the past, radiographic stents, which were later translated to surgical guides after cone-beam computed tomography (CBCT) scanning, were used to place implants (Misch, 2004). However, this approach is fraught with various technical laboratory procedures and errors in the placement of implants are a common consequence (Nickenig & Eitner, 2007). Digital surgical guides have since solved these problems by combining intraoral scans with CBCT images to plan implant positions according to the bone, soft tissue, and adjacent teeth (Ganz, 2015). These guides, if perfectly designed and fitted from the beginning to the end of the procedure, will allow for more accurate implant installation (Kim, Huh, & Yun, 2016).

Recently, technological progress in the digital era has allowed for the emergence of the static computer-assisted implant surgery (s-CAIS) that provides visualization of 3D bone, soft tissue and teeth morphology in the preoperative planning (Deeb et al., 2017;

Ozan et al., 2009; Whitley & Bencharit 2015). Some studies have compared the accuracy of implant position between preoperative and postoperative CBCT and concluded that s-CAIS has a good precision. Nevertheless, results diverge and cannot yet be universally applied due to the heterogeneity of study designs, most of which were in vitro experiments (Deeb et al., 2017).

Whereas, few clinical studies have reported about the accuracy of implant positioning in partially edentulous ridges. Besides, most of the accuracy studies have been still laboratory-based and have lacked clinical evidence (Ma et al., 2018). The accuracy of implants is generally assessed by comparison between primary and secondary surveyor. The primary outcome is the angular deviation (AD) and the secondary outcomes are the crestal global deviation (CGD), apical global deviation (AGD), vertical linear deviation (VLD), lateral linear deviation (LLD), apical vertical deviation (AVD), and apical lateral deviation (ALD) (Younes, Yildiz, Bouferguene, Ursi, & Brunharo, 2018).

## MATERIAL & METHODS

Inclusion criteria were as follows:

- Partially dentate adults with at least 6 remaining teeth
- The anticipated presence of sufficient bone volume allowing for implant placement with no simultaneous bone grafting
- Extractions within 2 months of welding.
- Want the missing tooth to be replaced by an implant
- Adequate related attached mucosa was found
- Mouth opening  $\geq$  40 mm
- Good oral hygiene
- Good general health

#### Exclusion criteria were as follows:

- Parafunctional habits
- Heavy smoking
- Physical or psychiatric disorders preventing the implant treatment.
- Previous radiotherapy of the head-neck region
- Younger than 18 years

#### Study design:

Researcher adopted pre and post Quasi-Experimental study design to fulfill the research objectives quantitatively. The Quasi-Experimental design is a popular design used in research. Pre/post-test design is a type of quasi-experimental study, in which an easily applied intervention can be studied in relationship to the group of subjects in the study. Conclusion Because the research design has problems that the validity of prepost and type study is not easily satisfied, we cannot expect it, but we can obtain associations in outcome measures in this popular research design by choosing randomization, controlling inner and external bias, and correctly applying simple statistics.

#### **Study setting:**

The current study conducted in dental implant clinic at Al-Azhar university. Data gathered from the patient by using CBCT before and after implant placement to compare the result between free hand, countersink guided vs implant placement with fully surgical guide.

#### **Data Collection procedure:**

#### **Analysis method:**

Free hand (countersink guided) and surgical guide surgeries were carried out by a parallel surgical kit (Dentsply®, MIS, M4, Germany), following the manufacturer's recommendations. The surgical guide surgeries were carried out using a dedicated (Dentsply®, MIS, M4 Germany) following the above-mentioned surgical plan. Both of the implants were performed for the same patient, on the same day and with the same devices. One implant per side was placed free hand, countersink guided and the other side with a computer-assisted implant guide.

With Blue Sky Plan 4 (Blue Sky Bio, Grayslake, IL, USA) software, the post-operative fixture was extracted as an STL file by segmentation the DICOM file of the CBCT taken after surgery used 3D slicer program as show in Figure 1.

Figure 1: show segmentation the DICOM file of the CBCT taken after surgery used 3D slicer program.

Then, the STL file post-operative fixture imported to Blue Sky Plan 4 program and superimposing with planned fixture on the CBCT on the planned implant location before surgery as presented in Figure 2.

Figure 2: show import the DICOM file post-operative fixture to Blue Sky Plan 4 program and superimposing with the CBCT which have the planned implant location before surgery.

More than twenty points marked on the two images using a point-based automatic image registration algorithm to ensure correspondence as show in Figure 3.

Figure 3 : aligned using a point-based automatic image registration algorithm.

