#### **Data Analysis**

The researcher employed the Statistical Package for the Social Sciences (SPSS) version 22 program for both data entry and statistical analysis. The data analysis process comprised two stages: first, descriptive analysis to summarize the data, followed by an inferential analysis that elucidated the relationships between the variables under investigation. Also, the Central tendency measures were performed to describe the collected data from patients. Exact Fisher's Test, Chi-square Test and Independent t-Test were used to examine the possible relationship between variables. The confidence interval was considered at 95% and a margin of error 5%. P-value less than 0.05 was considered to indicate a statistically significant difference.

Categorical outcomes were presented as absolute and relative frequencies. A bivariate analysis using Independent t-Test, or Fisher's exact test when application conditions were not achieved, was used to compare the groups. Differences between groups of scale variables were explored using parametric (Student's t test for independent or paired samples) or nonparametric tests. Chi square test was used to test the relationship between two categorical. In the present study the Independent t-Test, Fisher's exact test and Chi square test as well as median were used where the data was classified nonparametric.

Abbreviations:

Symbol	Description
СВСТ	Cone Beam Computed Tomography
CAD	Computer Aided Design
CAM	Computer-aided manufacturing
CAI	Computer Assisted Inspection
DICOM	Digital Imaging and Communications in Medicine
GIS	Guided Implant Surgery
STL	Standard Tessellation Language OR Standard Triangulated
AD	Angular deviation
CGD	crestal global deviation
VLD	Vertical Linear Deviation
LLD	Lateral Linear Deviation
AGD	apical global deviation
ALD	Apical Lateral Deviation
MS	Maxillary Sinus
IAN	Inferior Alveolar Nerve
s-CAIS	Static computer-assisted implant surgery
IOS	Intra oral scan
3D	Three-dimensional
FG	Fully guided
FH	Freehand
CS	Countersink
SD	Standard deviation
AVD	apical vertical deviation
FHM	free hand method
SGM	surgical guide method
FH	free hand

SG	surgical guide
PG	pilot guide
FG	fully guided

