## Ethics approval and consent to participate:

The study was designed as a Quasi-Experimental study including consecutive patients referred for implants and seeking treatment in four oral and maxillofacial surgery department (Clinics university). The study was approved by the Helsinki Committee Palestinian Health for Ethical Approval, Research Council (Number: PHRC/HC/1242/23) at its meeting on 23/02/2023 and implemented in strict adherence with ethical principles, that are on par with the World Medical Association's Declaration of Helsinki. Moreover, study goals were explained to patients. Privacy and confidentiality as well as voluntary participation were guaranteed. A consent form was signed by each patient enrolled in the present study.

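### The plan does not say how the guided side or the order of placement was decided in this split-mouth comparison, so choice of site could bias the technique contrast by an unknown amount

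*Combined protocol and SAP*

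**What the plan says.** The Abstract (Materials and methods) reports 30 implants, which "were placed in15 partially edentulous volunteers in need of implantation in the mandible or maxilla or both". The Analysis method section sets out a within-patient comparison: "Both of the implants were performed for the same patient, on the same day and with the same devices", and "One implant per side was placed free hand, countersink guided and the other side with a computer-assisted implant guide". It does not say who chose the side, by what rule, at what moment, or which implant went in first.

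On design, the Study design section states: "Researcher adopted pre and post Quasi-Experimental study design to fulfill the research objectives quantitatively". It goes on to concede that "the validity of prepost and type study is not easily satisfied, we cannot expect it, but we can obtain associations in outcome measures", and adds that this can be done "by choosing randomization, controlling inner and external bias, and correctly applying simple statistics". That is the only reference to randomization for this study; the other mentions concern cited work. No unit, list, concealment or assignment step accompanies it. The ethics section repeats the label: "The study was designed as a Quasi-Experimental study including consecutive patients referred for implants". Consecutive referral describes how patients enter, not which side receives which technique.

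For scale variables, the Data Analysis section names Student's "t test for independent or paired samples) or nonparametric tests". None of these tests contains a term for side, order or jaw.

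**The concern.** Pairing removes differences between patients. It does not remove differences between the two sites in one mouth. The Abstract allows implants in either jaw or both, and nothing in the text requires the two sites of a pair to be matched. If the operator decided the side, access, local bone, order of placement, or jaw where a pair spans both, could go with technique. The angular deviation contrast, which is the primary comparison, would then mix the effect of the guide with the effect of where and when it was used. A reader cannot tell whether side was randomized, alternated or chosen, and so cannot judge how far this applies.

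**Working it through.** **Count.** 15 patients x 2 implants = 30 implants, which matches the Abstract. The documents give no power calculation, standard deviation, site effect or split of sides, so everything below is an illustration on assumed values.

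**Systematic choice of site.** Suppose that in each mouth one site, on whichever side, gives s degrees more angular deviation with either technique. Let q be the fraction of patients whose guide went to that harder site. The paired difference (guided minus free hand) shifts by +s in a fraction q of patients and by -s in the rest:

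bias = s·q - s·(1 - q) = s(2q - 1)

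| q | s = 1 degree | s = 2 degrees |
|---|---|---|
| 0.5 | 0 | 0 |
| 0.6 | 0.2 | 0.4 |
| 2/3 | 0.33 | 0.67 |
| 0.8 | 0.6 | 1.2 |
| 1 | 1 | 2 |

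Below q = 0.5 the sign reverses and the bias favours the guide; at q = 0.2 it is -0.6 to -1.2 degrees.

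**Effect on the paired t-test.** Take no true technique effect, 15 pairs and a two-sided 5% level (the plan gives 0.05 but not the sidedness). With the guide at the harder site in 12 of 15 patients (q = 0.8), s of 1 to 2 degrees, and an assumed SD of the paired differences of 2 to 4 degrees apart from the site effect, the test rejects in 8% to 35% of simulated trials. A separate simulation with q = 0.75 and s equal to 0.25, 0.5 and 1.0 of that SD gives 7.4%, 13.5% and 29.1%.

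**What a concealed list would do.** If assignment is unrelated to which site is harder, the expected bias is 0. Chance error remains. When the harder side varies from patient to patient, the number k of guides at the harder site is Binomial(15, 0.5), and the error is s(2k - 15)/15:

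- SD = s/√15 = 0.26 degrees for s = 1 and 0.52 for s = 2.
- P(|2k - 15| ≤ 5) = 0.882 and P(|2k - 15| ≤ 7) = 0.965, so the 95th percentile of the absolute error is 7s/15 = 0.47 and 0.93 degrees.
- A split of 11:4 or worse on the harder site has probability 11.8%; 12:3 or worse, 3.5%.

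The paired standard error covers this chance error. In simulation with no technique effect, the paired t-test rejects in 4.9% to 5.1% of trials when the harder side varies between patients. When the harder site is always on the same side it rejects in 0.8% to 4.4%, which is conservative. The paired standard error does not cover a systematic choice.

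**Feasible balance.** Two sides x two orders = 4 combinations. In 15 patients the closest balance is 4/4/4/3, which gives 8:7 on side and 8:7 on order.

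**The case against.** The study does not present itself as a randomized trial. It uses the quasi-experimental label in three places, admits that validity is hard to secure, and speaks of associations. Site differences are also restrained by design: posterior sites (Aim), enough bone to avoid grafting (Inclusion criteria), and the same patient, day and devices (Analysis method). Each implant is measured against its own digital plan, so anatomy cannot enter angular deviation directly; it acts only through difficulty of execution. Finally, the methods are in the past tense, so a list may come too late.

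Most of this stands, and it limits the point. It does not remove it: a design label does not disclose an assignment rule, the reference to randomization remains unexplained, and restrained site differences are not absent ones.

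Three stronger readings are tempting and are not supported:

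- *That the operator did choose the side, or that the result is biased in favour of the guide.* The documents show neither. They are silent on the rule, and the sign of the bias depends on q.
- *That the nerve and sinus outcomes are contaminated by site anatomy.* This follows only if they are raw distances. The section on measuring the deviations words them as distances, but the Abstract counts them among nine measurements that represent deviations. The text leaves this unclear.
- *That a list would make the two groups of sites equal.* It balances side and order. Bone, access, jaw and tooth position are left to chance.

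**Conclusion.** The point holds as a gap in the assignment procedure that leaves the primary contrast open to selection of site. It is not a demonstrated bias. The omission is plain in the text available, though some pages were withheld from it. The size is conditional: 0.6 to 1.2 degrees if the harder site is worth 1 to 2 degrees and the guide went there in 80% of patients, and nothing if the choice was unrelated to difficulty. The values of s, q and the SD are assumptions, and the documents reveal neither magnitude nor direction. Reassurance from the paired standard error applies to chance imbalance only, and only if the paired option in the Data Analysis section is the one used. The change is worth making because it costs little, with medium confidence that it will matter.

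**What to change.** **For every patient not yet treated.** Once both sites are digitally planned and before the guide is made, assign the guided side and the order of placement from a concealed computer-generated list. Someone other than the operator should hold it, and it should be balanced over the four side-by-order combinations (4/4/4/3 if all 15 patients were still to come). Record side, jaw, tooth position and order, and report any departure from the list. State that it removes selection but not chance imbalance.

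**For patients already treated.** State in the Study design and Analysis method sections how side and order were chosen. Reconcile the reference to randomization with the quasi-experimental label. Tabulate side, jaw, tooth position and, if recorded, order by technique. Keep conclusions to association, as the Study design section already does, and do not describe non-randomized pairs as randomized. State also whether the nerve and sinus outcomes are raw distances or differences from plan.

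**Cost.** A list of at most 15 lines and a short amendment, with no extra patients, visits or procedures. The downside is that the operator gives up the choice of side. The document is dated 15 February 2023, before the ethics meeting of 23 February 2023, yet it describes the implants as already placed, so treatment status is unclear and the list may reach few patients or none. In that case the cost is one paragraph and one table.
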